7.4.4. End of Procedure

In all subjects, final angiography of the vessel(s) must be performed following intracoronary injection of nitroglycerin, isosorbide or dinitrate (see Table 7-2) and in the same views that were taken at baseline.

The end of the procedure is defined as the time the guide catheter is removed from the subject. If the subject is returned to the procedure room and a guiding catheter is

reinserted, a dilatation is performed, and an interventional device is inserted into the catheter, this should be considered a repeat intervention.

7.4.5. Bailout Procedures

In the event of a major dissection or an occlusive complication manifested as decreased target vessel flow, chest pain or ischemic ECG changes after index procedure that do not respond to repeat balloon inflations or intracoronary vasodilators (nitroglycerin, verapamil, diltiazem, nitroprusside), other bailout procedures may be performed, which may include additional stenting. Should an additional stent be used, it must be the assigned study stent unless clinically contraindicated. Multiple stenting with the Orsiro or Xience stents requires a 2-mm overlap. Such procedures must be documented in the eCRF.

All bailout procedures are considered adverse events (AEs) in this study. Bailouts procedures that result in any of the consequences characteristic of a serious adverse event (SAE) (e.g. death, prolonged hospitalization, etc. see Section 9.1.3) are considered SAEs.

7.4.6. Bailout-Staged Procedure

Planned staged procedures are not allowed in this clinical investigation. If during the intervention it becomes clinically necessary to postpone treatment of the second and/or third lesion to a later time point, this is regarded as a staged procedure and must be documented as such. For staged procedures, the use of an investigational stent is not allowed. Subjects requiring staged procedure should be treated according to the investigator's discretion and standard of care. These subjects should receive an approved, commercially available treatment and not a study stent.

All bailout procedures are considered adverse events (AEs) in this study.

7.5. Post-Procedure to Hospital Discharge

7.5.1. Immediately Post-Procedure

Immediately following the procedure:

- Heparin or bivalirudin should be discontinued.
- ACT should be monitored in accordance with hospital protocol.
- Vascular sheaths should be removed according to standard hospital practice.
- Approved vascular closure devices may be used at the discretion of the investigator in accordance with the manufacturer's instructions.

7.5.2. Clinical and Laboratory Assessments

The following clinical assessments and laboratory tests should be performed after the index procedure and before hospital discharge:

- Cardiac biomarkers CK and/ or CKMB (CKMB is required, or troponin if CKMB is not available) will be measured once within 6–24 hours post index procedure. CKMB or troponin is required.

Note: Every effort must be made to obtain cardiac biomarker values within the specified time ranges. Results of all cardiac biomarker measurements, even measurements performed outside the time range, will be documented in the medical record and reported on the eCRF.

If CKMB elevation (or troponin in the absence of CKMB) > 3x URL is noted post-procedure, CKMB (or troponin in the absence of CKMB) measurements should be performed every 4-12 hours and documented in the medical record and reported on the eCRF until values have returned to < 3x URL or until discharge, starting from when the first elevation is noted.

- A 12-lead ECG must be completed within 24 hours after the index procedure.
- Ischemic/angina assessment according to CCSC or Braunwald classification just prior to discharge.
- AE and SAE assessment.
- Anti-platelet/anti-coagulant medical therapy post procedure.
- Other cardiovascular and diabetic medications post procedure.

Prior to discharge, review of the study follow-up requirements with the subject is recommended to help ensure compliance with the follow-up schedule. In addition, confirmation of subject contact telephone numbers, including numbers for home, work numbers and primary physician, as applicable, should be completed.

7.6. Antiplatelet/Anticoagulation Regimen

Subjects will receive a minimum of 75 mg aspirin daily indefinitely, and 75 mg clopidogrel daily for a minimum of 6 months, 12 months are recommended for subjects who are not at high risk for bleeding.

Clopidogrel may be substituted with 5 mg or 10 mg prasugrel daily or 90 mg ticagrelor twice daily or 250 mg ticlopidine twice daily.

OUS investigators may follow medication administration recommendations in accordance with ESC guidelines, national guidelines and/or hospital standard of care.

7.7. Follow-Up Assessments

All randomized subjects will be followed through 5 years of follow-up, with assessments performed at 1 month, 6 months, 12 months and annually thereafter.

Subjects who are randomized, but do not receive a study stent (i.e., subjects who don't receive an Orsiro or Xience stent) will be followed for 12-months only.

An office visit is required for the 12-month follow-up visit. All other visits may be performed by telephone interview with the subject if the subject is unable to return for an office visit within the applicable follow-up window.

For each follow-up visit, all clinical assessments should be performed on the same date. Requirements of each follow-up evaluation are described below.

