validity of the primary endpoints when making decisions concerning subject exit. Study follow-up options and requirements for subjects exited from the study should be determined and applied to all subjects exited for similar reasons. Deviations in subject eligibility, as defined in the protocol, should be considered protocol violations and reported to the Institutional Review Board (IRB) or Ethics Committee (EC) immediately upon discovery, in accordance with local regulations. Subjects that are randomized, but do not receive a study stent during the index procedure post-randomization (e.g. unable to cross the lesion with the predilatation balloon or stent, randomization error, or lack of sufficient disease, etc.) may be exited from the study after completion of the primary endpoint visit assessments (12-month follow-up).

If a subject cannot continue to participate in the study but the investigator is able to maintain contact with the subject and they have not withdrawn consent to collect further data, then contact should be maintained per the original follow-up schedule and vital status data will be confirmed by the investigator and reported. For example, a subject may change geographic location or move into a nursing home, but may still remain in contact with the investigator. Identification of vital status will be handled at the investigational site level. Subjects have the right to discontinue from the study at any time or be discontinued at the investigator's discretion.

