## 2.6 Statistical Analysis Sets

### 2.6.1 Intention to Treat (ITT) Analysis Population

The Intent-to-Treat (ITT) population is defined as all randomized subjects. Subjects are analyzed according to the stent to which they were randomized (regardless of the actual stent that they received). This is the primary analysis population.

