## 2.9 Analysis of Secondary Endpoints

The secondary endpoints in the BIOFLOW-V study will be analyzed using frequentist methods. For each endpoint, the proportion and sample size will be calculated and reported for the Xience group and for the Orsiro group. Fisher’s exact test will be used to test the difference between the groups. Analyses of secondary endpoints will be carried out on the ITT, Modified ITT and PP analysis sets for BIOFLOW-V. However, there will be no direct imputation of missing data. Secondary Endpoints include the following measures:

- 1) Device success
- 2) Lesion success
- 3) Procedure success

BIOFLOW-V will utilize the percent residual stenosis, as assessed by the investigator for the primary analysis measure of the % residual stenosis for evaluating angiographic success for the aforementioned secondary endpoints. If investigator assessment of residual stenosis is not available, the in stent final % diameter stenosis as assessed by QCA will be used. MACE included in the procedure success will use the primary analysis definitions.

Treatment group difference (Orsiro minus Xience) in the success rates and the two-sided 95% confidence intervals of the difference will be presented.

The following secondary clinical endpoints will be evaluated prior to discharge, at 1-, 6- and 12-months and annually:

- 4) Death
- 5) Protocol-defined MI
- 6) Cardiac death or protocol-defined MI
- 7) MACE and individual MACE components
- 8) TLF and individual TLF components
- 9) TVF and individual TVF components
- 10) Stent thrombosis according to ARC criteria

Included in the analysis, will be subjects experiencing the event or who have adequate follow-up (e.g., at least 23 days for 1-month time point, at least 166 days for the 6-month time point, and at least 330 days for the 12-month time point).

All the re-adjudicated clinical endpoints in BIOFLOW-II and BIOFLOW-IV will be summarized by study and treatment group.

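### Follow-up stops at 12 months for randomized subjects who receive no study stent, so the 2- to 5-year results labelled ITT are not full ITT results

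*Protocol*

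**What the plan says.** Protocol 7.7 opens with the general rule: "All randomized subjects will be followed through 5 years of follow-up, with assessments performed at 1 month, 6 months, 12 months and annually thereafter". The synopsis says the same. The next sentence of 7.7 makes an exception: "Subjects who are randomized, but do not receive a study stent", defined as "subjects who don't receive an Orsiro or Xience stent", "will be followed for 12-months only". Protocol 5.3.2 treats the same group differently: they "may be exited from the study after completion of the primary endpoint visit assessments (12-month follow-up"). So 7.7 is mandatory and 5.3.2 permissive. Section 5.3.2 also says that nothing is collected after exit, and its own list of limited exit situations does not include the absence of a study stent.

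On the analysis side, SAP 2.6.1 states: "The Intent-to-Treat (ITT) population is defined as all randomized subjects". The randomization section of the protocol adds expressly that subjects who get no study stent are in the ITT population. SAP 1.4 evaluates death, MI, MACE, TLF, TVF and stent thrombosis annually to 5 years. SAP 2.9 does so on the ITT, modified ITT and PP sets, without direct imputation, under this rule: "Included in the analysis, will be subjects experiencing the event or who have adequate follow-up". Its day thresholds are examples that end at 12 months.

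**The concern.** ITT protects a comparison because every randomized subject is kept, whatever happens afterwards. Here the protocol itself ends data collection for part of the ITT set, while the SAP keeps the ITT label for years 2 to 5. This differs from ordinary attrition, which is unplanned.

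Who is affected is settled after randomization. Subjects are randomized once the guide wire has crossed the first lesion, before pre-dilatation and stent delivery. One listed reason for having no stent, failure to cross with the stent, can depend on the device.

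The SAP 2.9 denominator adds a second problem. After month 12, a non-stented subject with a first-year event still qualifies, and an event-free one does not. At stake are the long-term safety and efficacy comparisons, which are part of the study objective.

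**Working it through.** **Inputs from the documents.** Up to 1,400 randomized, 933 Orsiro and 467 Xience (Protocol 8). The plan's own figure reproduces: 1,260 / (1 − 0.10) = 1,400. Likewise 1,200 / 0.90 = 1,333.3, rounded up to 1,334.

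**Assumed inputs.** The documents give neither the non-stented share nor 5-year rates. I take a non-stented share of 1–3% per arm (5% as a stress case), a 5-year TLF rate of 15% in stented subjects, and the non-stented rates shown below.

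**Subjects affected.** 1% × 1,400 = 14; 3% × 1,400 = 42.

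**Formulas, per arm.** Let S be stented subjects, M non-stented subjects, e12 and e60 the non-stented TLF rates by month 12 and year 5, and 0.15 the stented 5-year rate.

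- Reported under SAP 2.9: (0.15·S + e12·M) / (S + e12·M)
- Full ITT: (0.15·S + e60·M) / (S + M)
- Bias in the difference (Orsiro − Xience): reported difference minus full-ITT difference. A positive value counts against Orsiro.

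**One arm worked through.** Orsiro with 3% non-stented: M = 28, S = 905, e12 = 20%.

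- Events kept: 0.20 × 28 = 5.6. Event-free subjects dropped: 22.4.
- Reported: (135.75 + 5.6) / (905 + 5.6) = 141.35 / 910.6 = 15.52%.
- Full ITT if e60 = 20% (no later events): 141.35 / 933 = 15.15%, an error of +0.37 points.
- Full ITT if e60 = 35%: (135.75 + 9.8) / 933 = 145.55 / 933 = 15.60%, an error of −0.08 points.
- The error is zero when e60 is near 32%: (0.1552 × 933 − 135.75) / 28 ≈ 0.32.

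With no non-stented Xience subjects (3% vs 0%), these errors are also the bias in the difference.

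**Both arms, arms of 933 and 467.**

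| Non-stented share, Orsiro vs Xience | Bias, e12 10%, e60 20% | Bias, e12 20%, e60 35% |
|---|---|---|
| 1% vs 1% | 0.00 | 0.00 |
| 3% vs 3% | 0.00 | 0.00 |
| 2% vs 1% | +0.04 | −0.03 |
| 3% vs 1% | +0.08 | −0.05 |
| 1% vs 3% | −0.08 | +0.05 |
| 5% vs 1% | +0.16 | −0.09 |

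**Extreme bound, 3% vs 1%.** Suppose all non-stented subjects are missing from the reported rate, every lost Orsiro subject has an event and no lost Xience subject does.

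- Full ITT, Orsiro: (135.75 + 28) / 933 = 17.55%.
- Full ITT, Xience: 0.15 × 462.33 / 467 = 14.85%.
- The true difference is 2.7 points; the reported difference is 15% − 15% = 0.

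**Primary endpoint.** It is assessed at 12 months, and 5.3.2 allows exit only after that visit. The effect is nil.

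**The case against.** Several points on the other side are sound.

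- A reader might infer that the loss depends on which device could not be delivered. The documents do not show that. Besides failure to cross with the stent, 5.3.2 lists a pre-dilatation balloon that cannot cross, randomization error and insufficient disease, none of which is tied to the assigned stent. The rule also turns on receiving either study stent, so a subject given the other arm's stent stays in follow-up. Dependence on the device is possible, not established.
- A reader might set the reported 15.5% against the 15.0% of stented subjects and infer a half-point artefact against Orsiro. That comparator is wrong. The target is the full ITT rate, which includes the non-stented subjects' own later events, and against it the sign can go either way.
- The event-or-follow-up denominator affects every early exit, and its use beyond 12 months is an inference, because the thresholds in SAP 2.9 are only examples.
- Protocol 8.10 plans a supplementary Cox analysis that includes all subjects and censors at last follow-up, which would avoid the event-dependent denominator. SAP 2.9 does not carry it forward; the exponential model in SAP 2.8 serves the primary endpoint only.
- Section 5.3.2 asks for continued contact with subjects who cannot continue but have not withdrawn consent. That would recover vital status only, and it does not clearly cover subjects released by the 12-month rule.

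These limit the size and certainty of the problem. They do not remove the conflict between the follow-up rule and the ITT label.

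**Conclusion.** The point holds for the secondary endpoints after month 12. Sections 7.7 and 5.3.2 disagree on whether exit is required. Either version leaves the annual ITT results for years 2 to 5 without some randomized subjects by design, selected by an event after randomization.

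The likely numerical effect is small: near zero with equal non-stented shares, and roughly 0.1 to 0.4 points of unknown sign with unequal shares in the 0–3% range. It comes close to 3 points only when nearly all lost outcomes go against one arm. These sizes rest on assumed shares and event rates. Once follow-up has stopped, the trial's own data cannot show which case applies. The 12-month primary analysis and its sample size are untouched. The change is worth making because it is cheap and restores the comparison the plan names.

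**What to change.** Delete the 12-month stop in Protocol 7.7 and the matching sentence in 5.3.2. Follow every randomized subject to 5 years by the telephone contact already allowed for years 2 to 5. The cost is a short amendment and four contacts per subject: 4 × 14 = 56 to 4 × 42 = 168 in all on the assumed range. The downside is having to retain a few dozen subjects who carry no study device.

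If follow-up has already ended for some, amend SAP 2.9 to:

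- add a time-to-event analysis, as in Protocol 8.10, that includes all ITT subjects and censors at last follow-up;
- state that ITT follow-up after month 12 is incomplete by design;
- report the number of non-stented subjects and the reasons, by arm.

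Censoring uses each subject's observed time but does not recover the missing years. It assumes that those who left have the same later risk as those who stayed. Relabelling years 2 to 5 as modified ITT is not an adequate substitute. That set requires the assigned stent, so it also drops subjects who got the other arm's stent and are still followed.

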7.7.1. One (1) Month Clinical Follow-Up (30 ± 7 Days)

Subjects will be evaluated at 1 month post-procedure (± 7 days) by a telephone interview and/or an office visit. The following assessments must be completed:

- Ischemic/anginal status (according to CCSC or Braunwald).
- AEs and SAEs since discharge.
- Anti-platelet/anti-coagulant medical therapy since discharge.
- Other cardiovascular and diabetic medications since discharge.
- Any coronary intervention (e.g., repeat revascularization) that occurred since the post-procedure discharge.
- 12-lead ECG (if an office visit is performed).

7.7.2. Six (6) Month Clinical Follow-Up (180 ± 14 Days)

Subjects will be evaluated at 6 months post-procedure (180 ± 14 days) by a telephone interview or an office visit. The following assessments must be completed:

- Ischemic/anginal status (according to CCSC or Braunwald).
- AEs and SAEs since the previous contact.
- Anti-platelet/anti-coagulant medical therapy since the previous contact.
- Other cardiovascular and diabetic medications since the previous contact.
- Any coronary intervention (e.g., repeat revascularization) that occurred since the previous contact.
- 12-lead ECG (if an office visit is performed).

7.7.3. Twelve (12) Month Clinic Visit (360 ± 30 Days)

Subjects will be evaluated at 12 months post-procedure (360 ± 30 days). The 12-month follow-up is required to be an office visit with the subject. During the 12-month follow-up visit, the following assessments must be completed:

- Ischemic/anginal status (according to CCSC or Braunwald).
- AEs and SAEs since the previous contact.
- Anti-platelet/anti-coagulant medical therapy since the previous contact.
- Other cardiovascular and diabetic medications since the previous contact.
- Any coronary intervention (e.g., repeat revascularization) that occurred since the previous contact.
- 12-lead ECG.

7.7.4. Long-Term Clinical Follow-Up at 2, 3, 4 and 5 Years Post-Procedure (Annually \pm 60 Days)

Subjects will be evaluated at 2, 3, 4 and 5 years post-procedure (\pm 60 days) by a telephone interview and/or an office visit. The following assessments must be completed:

- Ischemic/anginal status (according to CCSC or Braunwald).
- AEs and SAEs since the previous contact.

Note: All AEs (serious and non-serious) will be reported for the entire study period to the extent required by national and/or local requirements. For US sites only: After the 12-month follow-up visit, continuing AEs will be followed through to resolution or until event becomes stable and only serious adverse events, including MACE and clinical study endpoints, will be recorded.

- Anti-platelet/anti-coagulant medical therapy since the previous contact.
- Other cardiovascular and diabetic medications since the previous contact.
- Any coronary intervention (e.g., repeat revascularization) that occurred since the previous contact.

7.8. Unscheduled Study Visit

Subjects may present to the clinic outside of the scheduled follow-up windows. Such unscheduled study visits will be reported if the subject has experienced an AE. For an unscheduled study visit, concomitant cardiac medications and data regarding adverse events will be collected.

Subjects assessed at an unscheduled study visit may require diagnostic testing (e.g. ECG, angiogram, CK/CKMB levels) and/or a revascularization procedure to further evaluate and treat ischemic symptoms. Any repeat procedure must be reported on the relevant case report forms, including any unscheduled visits prior to the repeat procedure and/or adverse events associated with the procedure. Only commercially available stents are allowed during repeat procedures. Use of investigational stents is not permitted.

Any repeat or unscheduled diagnostic or interventional coronary revascularization procedure performed should include a diagnostic assessment of the target lesion(s) and investigational stent(s). Angiographic data collected during any repeat procedure on the target vessel(s) must be made available to the CEC for an independent review and assessment. Likewise, the angiographic images should be submitted to the core laboratory for an independent review and assessment of the target lesion and investigational stent.

7.9. Angiographic Core Laboratory

The angiographic core laboratory will provide sites with a written procedural manual describing the acquisition and submission procedures for the baseline and subsequent

repeat angiograms. Sites will be requested to obtain and submit a minimum of two orthogonal views at baseline and post-procedure in accordance with the manual.

Baseline and procedural angiograms for all subjects will be sent to the independent angiographic core laboratory for evaluation. In addition, any coronary angiograms performed during the trial follow-up period due to suspicion of restenosis of the target lesion(s) will be forwarded to the angiographic core laboratory for analysis.

8. STATISTICAL CONSIDERATIONS AND ANALYSIS PLAN

The BIOFLOW-V clinical trial is a prospective, multicenter, randomized, controlled study. A total of up to 1,400 subjects will be randomized, stratified by study center, in a 2:1 ratio with 933 subjects randomized to receive the Orsiro stent and 467 subjects randomized to receive the Xience stent.

The trial is designed to assess the non-inferiority of the Orsiro stent compared to the Xience stent with respect to the primary endpoint of 12-month TLF, defined as cardiac death, target vessel Q-wave or non-Q-wave MI, or any clinically-driven TLR.

For this purpose, data from BIOFLOW-V randomized subjects will be combined with data from historical subjects from the BIOFLOW-II and BIOFLOW-IV randomized trials employing a Bayesian approach. Only subjects who meet all clinical and angiographic eligibility criteria of the BIOFLOW-V trial will be included in the analysis.

8.1. Prior Data

The Orsiro clinical trial program includes BIOFLOW-II, BIOFLOW-IV and BIOSCIENCE, three randomized controlled trials in which subjects were randomized to the Orsiro stent against the Xience Prime™ or Xience Xpedition™ stents. A brief description of these trials is provided in Section 3.5. The inclusion and exclusion criteria for BIOFLOW-II and BIOFLOW-IV are nearly identical to those proposed for BIOFLOW-V, whereas the inclusion and exclusion criteria in BIOSCIENCE were more liberal to allow enrollment of a broadly inclusive real world population. We propose to use data from the BIOFLOW-II and BIOFLOW-IV trials prospectively using a Bayesian approach in the final non-inferiority analysis of the BIOFLOW-V study. A summary of the comparison of the study design of BIOFLOW-II and -IV trials along with the proposed BIOFLOW-V study can be found in Table 8-1. The current status of the studies is as follows:

- BIOFLOW-II – Enrollment into the trial was completed and 12-month results are available. A total of 298 subjects were randomized to receive the Orsiro stent and 154 were randomized to receive the Xience Prime™ stent. Of them, 287 Orsiro subjects and 148 Xience subjects completed their 12-month follow-up.
- BIOFLOW-IV - Enrollment into the trial is still ongoing and it is anticipated that 370 Orsiro subjects and 185 Xience Prime™/Xpedition™ subjects will be contributed from this trial.

To ensure the validity of data from subjects across trials, the following measures will be taken:

- Only subjects that meet all BIOFLOW-V clinical and angiographic eligibility criteria will be included.
- Evaluation of the 12-month TLF rate (a primary endpoint in the BIOFLOW-V trial and a secondary endpoint in the BIOFLOW-II and BIOFLOW-IV trials) will be performed in a uniform fashion, using a consistent set of definitions and similar follow-up schedule:
 - The measurement schedule of cardiac enzymes is similar in all trials: cardiac enzymes are collected once within 6-24 hours post index procedure. While all trials mandated collection of CK and CKMB, the BIOFLOW-II also mandated measurement of troponin. The BIOFLOW-IV and BIOFLOW-V trials allow measurement of troponin if CK and CKMB are not used. To address the differences in the collection of cardiac enzymes between the three trials, a uniform definition of peri-procedural MI that is based on CK and CKMB levels (with troponin levels used only in the absence of CK and CKMB) will be utilized.
 - All trials have similar clinical follow-up schedule at 1 month (telephone contact/clinic visit), 6 months (telephone contact/clinic visit) and 12 months (telephone contact/clinic visit for BIOFLOW-II clinic visit for BIOFLOW-IV and BIOFLOW-V).
 - The BIOFLOW-II and BIOFLOW-IV trials used the same independent angiographic core laboratory. To ensure consistency, angiograms from the BIOFLOW-II, BIOFLOW-IV and BIOFLOW-V trials will be analyzed or validated by the same angiographic core laboratory.
 - All clinical endpoints (potential TLR, MI and death events) will be re-adjudicated by the same independent CEC as will be employed for the BIOFLOW-V data, using uniform definitions.
- Data quality will be confirmed in accordance with the monitoring plan of each trial.

Table 8-1. Subjects' Poolability

	BIOFLOW-II	BIOFLOW-IV	BIOFLOW-V
Eligibility Criteria	All subjects will match BIOFLOW-V clinical and angiographic inclusion/exclusion criteria		
Primary or Secondary Endpoint Definition	TLF: cardiac death, target vessel Q-wave or non-Q wave MI, CABG, clinically driven TLR		
Follow-up schedule	1mo, 6mo, 9mo angio, 12mo , 2yr, 3yr, 4yr, 5yr	1mo, 6mo, 12mo , 2yr, 3yr, 4yr, 5yr	1mo, 12mo , 2yr, 3yr, 4yr, 5yr
Enzyme measurements	CK, CKMB (optional) and Troponin: 
 • Baseline • Within 6-24 hours after the index procedure or at discharge, whichever comes first 	CK, CKMB (optional) or Troponin (if CK and CK-MB are not used): 
 • Baseline • Within 6-24 hours after the index procedure or at discharge, whichever comes first 	CK, CK-MB, Troponin (if CKMB is not available): 
 • Baseline • Within 6-24 hours after the index procedure
Clinical Monitoring	
 • 100% source verification • Independent core labs for angiography, IVUS & OCT • On-site monitoring • Independent CEC adjudication 	
 • 100% source verification • Independent angiographic core lab • On-site monitoring • Independent CEC adjudication 	
 • 100% source verification • Independent angiographic core lab • On-site monitoring • Independent CEC adjudication

